In addition to the potential relationship with body composition, fat oxidation at rest and during exercise is known to be influenced by numerous other factors including nutritional status [12, 50, 51], sex [52-54], exercise mode [53], skeletal muscle fibre composition and glycogen content [55] physical activity level (self-reported) [54, 55] and cardiorespiratory fitness [54, 56, 57]. However, there is reportedly large inter-individual variability in fat oxidation at rest [55] and during exercise [54, 55, 58]. While the above factors may partly account for the inter-individual variability reported, large amounts of variance remains apparently unaccounted for e.g. up to 87% in peak fat use during exercise ($\text{mg} \cdot \text{kg fat free mass}^{-1} \cdot \text{min}^{-1}$) [54]. Furthermore, such previous studies have typically recruited small samples of young, healthy active individuals, who were also predominantly male, limiting the generalisability of previous findings to the wider population. We want to investigate a comprehensive range of novel and unexplored variables (e.g. sex hormone concentrations, and skeletal muscle and adipose tissue characteristics) alongside previously identified 'determinants' of fat oxidation at rest and

during exercise in a wide range of adults. This will provide us with a more holistic and broad view, allowing determinants to be identified independently of a comprehensive range of measured lifestyle, personal, metabolic, genetic and physiological characteristics.

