Lastly, this study will also address the intra-individual variability and reliability of fat oxidation at rest and during exercise by asking individuals to complete two identical main trial days 7 – 14 days apart. Intra-individual variability has become a recent topic of great interest in metabolism research [59-61]. The few studies to date that have investigated the intra-individual variability of fat use during exercise are not only confounded by the above recruitment issues, but have also not reported data on an individual level or systematically applied the wide range of reliability statistical methods available [15, 62-68]. Intra-individual variability may partially account for the previously reported inter-individual variability in fat use and thus, only once accounted for can determinants of fat use be more precisely determined. Importantly, this has not previously been considered in determinant studies. Thus, we will apply the entire range of reliability statistical methods available to assess intra-individual variability and when reporting the results of the current study, will plot anonymous individual data alongside group means. This will provide a highly systematic and valid evaluation of the reliability and intra-individual variability of fat use at rest and during exercise alongside drawing firmer conclusions on potential determinants.

Overall, this project will extensively explore fat oxidation in a wide range of ‘healthy’ and ‘at risk of metabolic disease’ adults under two proposed metabolic flexibility paradigms; post-absorptive resting and exercising conditions. This will provide important insights into fat use at rest and during exercise, help evaluate current and future research, and aide in the design of future nutrition and exercise interventions to improve human health.

Study Aims / Objectives:

Therefore, the objectives of this study are to comprehensively and systematically explore whether whole-body fat use at rest and during exercise is:

- 1) Altered in individuals with overweight or obesity compared to lean individuals
- 2) Associated with a wide range of physiological, metabolic, lifestyle and genetic variables (i.e. potential determinants or health outcomes)
- 3) The true inter- and intra-individual variation in fat use which will help to more confidently determine the above objectives.

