- 4) Conduct sub-group analyses to explore any moderators on the association between potential determinants and fat use e.g. sex, diet status (e.g. High CHO Vs Low CHO dietary intake), menstrual cycle (females only) and sex hormone thresholds.

Study Design:

This study proposed is an observational, exploratory cross-sectional study that plans to recruit a total of 200 male and female adults aged between 18 – 65 years, who are classed as either ‘healthy’ or ‘at-risk of metabolic disease’. Participants will visit a laboratory at the University of Bath on four occasions. All visits will take place at a Department for Health Laboratory on the University of Bath Main Campus. Please see figures 1 and 2 for a study outline and schematic, respectively.

Following advertisement of the study, interested participants will be asked to contact the Chief Investigator ([name] [CI]) for further information via email/telephone correspondence. If after reading the information sheet, the potential participant is still interested in partaking, they will be invited to attend a preliminary meeting at the University of Bath Main Campus to further discuss the trial (Visit 1).

Visit 1 (approx. 45 minutes)

After the potential prospective participant has read the information sheet, seen the study flowchart / schematic outlining the protocol and study demands, had any questions answered and are able to competently describe back the study to the CI, they will be asked to sign two consent forms (one copy for them, one copy for the CI) if they are still interested in partaking. Study eligibility and health screening (via questionnaires) will then be assessed and if eligible, a short familiarisation process will take place and a demographic and lifestyle questionnaire completed. The familiarisation process involves breathing through a mouthpiece for 5 minutes

and 10 minutes of very low intensity cycling (at 30, 40 and 65-Watts). This is in an attempt to increase the accuracy of data obtained on each main trial day (Visit 2 and 3). Dates will then be scheduled for Visit 2, 3 and 4 and the collection of the preliminary main trial day lifestyle measurements (diet and physical activity monitoring). For female participants who are eumenorrheic or oligomenorrheic and not using contraception (i.e. combined pill, intrauterine device), Visit 2 and 3 will be scheduled to be completed in the same stage of the menstrual cycle via the self-reported menstrual cycle questionnaire.

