	Fasting measures of Adipokines: Leptin, Adiponectin
	Fasting measures of Catecholamines: epinephrine and norepinephrine
	Fasting measures of sex hormones: 17 beta-estradiol, testosterone, progesterone
	Fasting pancreatic derived hormone concentrations: insulin and glucagon
	Hydration Status: Urine Specific Gravity
	Age (years)
	Sex
	Ethnicity
	Smoking Status
	Medication / Supplement Use
	Dietary Patterns / Requirements
	Body Fat Percentage
	Lean Body Mass (kg)
	Body Fat Distribution
	Waist and Hip Circumference
	Fat Mass Index
	Genotype analysis
	Skeletal Muscle Characteristics (Protein Content and / or Activity)
	Adipose Tissue Characteristics (Protein Content and / or Activity)

Data will be checked for normal distribution prior to analysis via Shapiro-Wilk's normality test and visual inspection of histograms. Parametric tests will be conducted on normally distributed data. Non-normally distributed data will be log-transformed if appropriate or the equivalent

non-parametric tests will be conducted. Statistical significance will be set at $P < 0.05$. The statistical analysis for the study objectives identified above are as follows:

- 1) The effect of body composition on whole-body fat use will be tested by separating groups into defined categories (e.g. lean, overweight or obese) and conducting a one-way ANOVA and mixed design model. The latter to test for any interaction effects across the two main trial days.
- 2) To identify determinants / characteristics that may be associated with whole-body fat use, correlation analysis will firstly be conducted between whole-body fat use at rest and during exercise with each variable. Statistically significant correlates will then be added to a follow-up hierarchical regression analysis to predict whole-body fat use at rest and during exercise.
- 3) At a group level, intra-individual variation in whole-body fat use will be tested by a paired sample t-test. A range of further reliability / variability tests will be conducted to comprehensively determine intra-individual variation: Pearson correlation coefficient, Intra Class Correlation, Coefficient of Variation, Bland-Altman plots with 95% Limits of Agreement and Typical Error. Additionally, individual data will be plotted on graphs alongside group means.

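### Objective 2 screens about 32–36 variables at unadjusted P<0.05 and refits the significant ones in the same participants, so the final P values and R² are nominal and should be reported as such

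*Combined protocol and SAP*

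**What the plan says.** All references are to the combined protocol and SAP.

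- **Threshold** (Statistical / Data Analysis): "Statistical significance will be set at" P < 0.05. No adjustment is given.
- **Step 1** (item 2): "correlation analysis will firstly be conducted between whole-body fat use at rest and during exercise with each variable".
- **Step 2** (item 2): "Statistically significant correlates will then be added to a follow-up hierarchical regression analysis". No separate sample is named, and no block order or set of forced-in variables is given.
- **Status** (Study Design): an "observational, exploratory cross-sectional study that plans to recruit a total of 200 male and female adults".
- **Ambition** (background text before the aims): "We want to investigate a comprehensive range of novel and unexplored variables", with the wide range of measures "allowing determinants to be identified independently of a comprehensive range of measured lifestyle" and other characteristics. The paragraph on repeat testing adds "alongside drawing firmer conclusions on potential determinants".
- **Prior knowledge** (background): fat oxidation "is known to be influenced by numerous other factors including nutritional status" and several others, so a complete absence of real determinants is not expected.

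The document names no multiplicity control, hold-out sample, cross-validation, shrinkage or caution on reading the final P values.

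**The concern.** A variable enters the regression because its correlation with the outcome was significant in these participants. Testing it again in the same data is not a fresh test. The regression P value takes no account of the number of variables screened or of the selection, and R² is computed on the data that chose the predictors. Readers are likely to take the final table as a list of independent determinants with valid P values, and nothing in the plan would tell them otherwise. Objective 2 is a main aim and this table is its principal output.

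**Working it through.** **The plan's own figures.** Sample Size Estimation uses R² of 36% and 13%. With f² = R²/(1−R²), these are 0.36/0.64 = 0.5625 and 0.13/0.87 = 0.1494. The overall F test (noncentrality f²N, alpha 0.05, power 95%) gives N = 42 with five predictors and N = 119 with three, matching the plan. The predictor counts are inferred, because the plan does not state them. Ten predictors with f² = 0.15 need 172, and 180–190 gives power of 96.0–97.0%, consistent with the chart reading. These calculations are not in dispute. They describe a model whose predictors are fixed beforehand, not a screen.

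**Number of candidates.** The document states none, so this is a tally of the outcome table without its seven fat-oxidation and FATmax entries.
- Table rows: 26.
- Replace the five rows that name several analytes by those analytes (5 metabolites, 2 adipokines, 2 catecholamines, 3 sex hormones, 2 pancreatic hormones = 14): 26 − 5 + 14 = 35.
- Waist and hip counted separately: 36.
- From 35, drop the two optional-biopsy rows and count menstrual status under sex hormones: 32.

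Macronutrients and genotype count as one each, which leans low.

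**Screen alone, no true association, independent tests.** The chance of at least one false correlate per outcome is 1 − 0.95^k: 73.7% for k = 26, 80.6% for 32, 83.4% for 35 and 84.2% for 36. The screen runs for both rest and exercise.

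**Both steps, by simulation.** Inputs from the plan: n = 200, P<0.05, R² of 13% and 36%. Assumptions: 35 continuous candidates, the correlation structures shown, and either no true determinant or three with equal effects. All screened-in variables are entered; the last step of a hierarchical regression on the same variables gives the same coefficients, P values and R².

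| Correlation among candidates | No true determinant: significant model | R² 13%: at least one false determinant | R² 36%: at least one false determinant |
|---|---|---|---|
| Independent | 84% | 64% | 49% |
| Blocks of five at 0.3 | 80% | 55% | 42% |
| Blocks of five at 0.6 | 68% | 39% | 42% |
| Blocks of seven at 0.7 | 49% | 35% | 54% |
| Every pair 0.3 | 67% | 23% | 66% |
| Every pair 0.5 | 36% | 54% | 79% |

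Repeat runs agree to within about four points. Across runs, the 13% column spans 22–66%.

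**Comparators with three true variables.**
- Ten pre-named predictors, three of them true, list a false determinant in 27–30% of studies. Theory for seven null predictors: 1 − 0.95^7 = 30%.
- All 35 entered without a screen: 75–78%.
- The chance that any one null variable is named after the screen was 0.8–4.9% across the settings.

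**What selection does to the final P values.** With no true association and 32 or 36 independent candidates, 82–83% of the coefficients that reach the model have P<0.05, against a nominal 5%. If every pair correlates 0.3, it is 29–31%. This is a benchmark; the share falls as candidates overlap.

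**R², independent candidates.** Apparent against out-of-sample: 0.17 against 0.064 at a true 13%, and 0.385 against 0.326 at 36%. Ten fixed predictors have apparent R² of 0.17 and 0.39.

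**Forced first block.** Entering four named variables first leaves the false-determinant rate at 38–67% (13%) or 43–54% (36%) for independent or five-variable-block candidates. The plan's silence on blocks therefore does not change the conclusion.

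**The case against.** **The study is exploratory, and its language is hedged.** This stands in part. Objective 2 speaks of potential determinants or health outcomes, and item 2 of characteristics that may be associated with fat use. The phrase on firmer conclusions concerns potential determinants and sits in the argument for repeat testing. A reader might infer that the plan promises confirmed determinants, but the text does not go that far: in the background, independence means adjustment for other measured characteristics. The framing justifies screening. It does not turn nominal P values into valid ones.

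**The false-determinant rates are not caused by selection.** Largely right. A reader might take 22–66% as the damage done by screening. The comparators do not support that: in the independent and block structures the screen lists false determinants less often than the unscreened full model, and no single null variable is named more than about 5% of the time. The rates mostly measure many tests without multiplicity control.

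**Any ten-predictor model overstates R².** Conceded. A reader might infer that the screen itself inflates R², but ten fixed predictors have a similar apparent R². Out of sample at 13%, they reach 0.08 if all three true variables are named and 0.03 if one is missed, against 0.064 for the screen. A model limited to pre-named variables is therefore not clearly better.

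**The simulation is simplified.** Also right. The table is headed as outcome measures, not as a list of regression candidates. Sex, ethnicity, smoking and genotype are categorical, menstrual status applies to women only, and biopsies are optional. These points affect the exact percentages; even 26 independent tests leave a 73.7% chance of a false correlate.

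**Conclusion.** The point holds as a reporting defect. Item 2 will produce P values and an R² that ignore both the number of variables tested and their selection in the same data, and the plan neither corrects this nor says so. With no true determinant, a nominally significant model appears in about 36–83% of studies against 5%. That is a benchmark only, because the background lists known influences. With three true variables explaining 13%, the figure that Sample Size Estimation gives for the primary outcome's units, 22–66% of studies list at least one false determinant, mainly through unadjusted multiple testing. The R² gap is real but shared with fixed models of similar size.

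The rates rest on the tally of 35 candidates, assumed correlations and assumed effects; only n, the threshold and the two R² values come from the plan. Severity lies between a point to consider and a low-priority correction. The screen is a reasonable choice for this study, and neither the design nor the sample size is called into question.

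**What to change.** Keep the screen and the P<0.05 entry rule. Add three sentences to item 2:

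1. Univariate correlations are reported with Benjamini-Hochberg q values for each outcome, for information and not as a rule for naming determinants.
2. Final-model P values are reported as exploratory and not adjusted for multiplicity or selection.
3. Beside the apparent R², an R² is reported from 10-fold cross-validation that repeats the whole screen in each fold.

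Repeating the screen matters. At a true 13% with independent candidates, whole-procedure cross-validation gave 0.056 against an actual 0.065, whereas cross-validating only the final model gave 0.131. With no true determinant the whole-procedure figure was −0.05 against −0.05; the final-model-only figure was +0.03.

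The q values should not decide which variables are called determinants. A q≤0.10 rule would cut true variables named from 2.46 to 1.81 of three (13%, independent) and leaves the false-determinant rate unchanged at 53% for blocks of seven at 0.7 with R² 36%.

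Costs: three sentences and modest code, with no change to data collection. The reported R² will be lower, and it is imprecise in a single study (SD about 0.06–0.07, as large as the value itself at 13%). The q values help little when candidates are strongly correlated, so the label in sentence 2 is needed regardless.

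### Known determinants enter the regression only if their unadjusted correlation is significant, so adjustment for them, and the independence promised, is not assured

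*Combined protocol and SAP*

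**What the plan says.** Item 2 of Statistical / Data Analysis has two steps. First, "correlation analysis will firstly be conducted between whole-body fat use at rest and during exercise with each variable". Then: "Statistically significant correlates will then be added to a follow-up hierarchical regression analysis to predict whole-body fat use at rest and during exercise". The section sets one significance level, P < 0.05. It names no variable for entry regardless of its correlation, and it gives no order of blocks.

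The background, ahead of Study Aims / Objectives, states that "fat oxidation at rest and during exercise is known to be influenced by numerous other factors including nutritional status". The same sentence goes on to list sex, self-reported physical activity and cardiorespiratory fitness, among others. The background then presents the breadth of measurement as "allowing determinants to be identified independently of a comprehensive range of measured lifestyle, personal, metabolic, genetic and physiological characteristics".

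No other part of the plan supplies the adjustment. Item 1 compares body-composition categories by one-way ANOVA and a mixed model, with no covariates named. Objective 4 plans subgroup analyses of moderators such as sex and diet status.

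**The concern.** Whether a variable must be adjusted for depends on its relation to the outcome and also on its relation to the other predictors. A crude P value reflects the two mixed together. When two real determinants are correlated and pull in offsetting directions, each one's crude correlation shrinks towards zero. A determinant that the protocol itself regards as established can then be discarded before any adjusted model is fitted. Whatever stays in the model is left unadjusted for it.

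What is at stake is the interpretation of objective 2. A variable reported as a determinant may partly carry the effect of a known factor that was screened out, and a real determinant may be reported as unrelated. The background gives its own example of entangled predictors: it cites two small studies suggesting that adiposity may not affect fuel use once fitness is allowed for.

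**Working it through.** **The plan's own figures.** The documents give no figure for the screening rule. The nearest are in Sample Size Estimation, and they are not in dispute. Using the overall F test of R², 95% power for R² = 0.36 needs 42 participants with five predictors, and for R² = 0.13 it needs 119 with three (the predictor counts are not stated). For a medium effect (f² = 0.15) with ten predictors, power is 96.0% at 180 and 97.0% at 190, which agrees with the plan's statement of more than 95%.

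**Inputs.** n = 190, the upper end of the plan's 180-190. Entry is at two-sided P < 0.05 (sidedness is not stated). Two determinants, labelled VO2peak and sex, have standardised partial effects b1 and b2 and correlation ρ. The documents give none of these three values, so they are assumptions shown over a range. Sex is coded ±1, so an effect of 0.3 means a 0.6 SD difference between the sexes.

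**Step 1, the threshold.** |r| must exceed t/√(n − 2 + t²) = 1.973/√(188 + 3.89) = 0.142.

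**Step 2, the crude correlation.** For VO2peak, r = b1 + ρ·b2. With 0.3, 0.3 and ρ = -0.5, r = 0.3 − 0.15 = 0.15, barely above the threshold.

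**Step 3, the chance of being dropped.** By Fisher's transformation, with SE = 1/√187 = 0.0731 and atanh(0.142) = 0.143, the chance is about Φ[(0.143 − atanh r)/0.0731]. For r = 0.12 this is Φ[(0.143 − 0.121)/0.0731], or about 62%. For r = 0.15, 0.21, 0.30 and 0.25 it is about 46%, 17%, 1% and 6%.

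**Step 4, simulation of the whole rule.** Repeat runs agree to within about two percentage points.

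| VO2peak, sex, ρ | Crude r, VO2peak | VO2peak dropped | VO2peak detected, both in model | Both fail | Both enter |
|---|---|---|---|---|---|
| 0.3, 0.3, -0.6 | 0.12 | 61% | 92% | 30% | 6% |
| 0.3, 0.3, -0.5 | 0.15 | 45% | 96% | 12% | 22% |
| 0.3, 0.3, -0.3 | 0.21 | 18% | 98% | 1% | 68% |
| 0.3, 0.3, 0 | 0.30 | 1% | 99% | 0% | 98% |
| 0.4, 0.3, -0.5 | 0.25 | 6% | over 99% | 2% | 24% |

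**Step 5, the coefficient that survives.** In the last row VO2peak nearly always passes, but the crude correlation for sex is 0.3 − 0.5 × 0.4 = 0.10, so sex usually fails. Without sex in the model, the expected VO2peak slope is 0.40 − 0.5 × 0.3 = 0.25. Averaged over the studies in which VO2peak enters alone, it is 0.27 instead of 0.40.

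**Step 6, what forcing variables in costs.** At N = 200, the 1-df power for a partial f² of 0.02 falls from 51.2% with one predictor in the model to 49.4% with ten. The overall test of R² = 0.13 with ten predictors needs N = 173. These figures count degrees of freedom only and leave collinearity out.

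**The case against.** The strongest reply is that masking needs correlated predictors with offsetting effects, and the documents give neither correlations nor directions for any pair. With uncorrelated predictors, or effects that reinforce each other, the screen loses almost nothing. That stands, and it makes this a conditional risk. A reader might infer that known determinants will cancel each other out in this study; the text does not support that.

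Three further replies stand in part:

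- **Mutual adjustment.** Retained correlates are adjusted for one another, objective 2 itself speaks only of association, and the study calls itself exploratory. It would be too strong to say that independence is not delivered at all. But the background does promise it, and an exploratory aim justifies screening novel candidates rather than factors already called known.
- **Subgroups.** Within one sex, sex cannot mask VO2peak. With about 95 people of one sex, a correlation would detect VO2peak in 66-73% of studies under the first two scenarios. This is not adjustment, and item 2 does not feed it into the screen.
- **Collinearity.** The 92-99% comes from a two-variable model. With age, activity and diet added, and assumed within-sex correlations with VO2peak of 0.6 for activity and -0.4 for age, detection in the first two scenarios falls to 71-79%. That is a real cost, though still well above the 39% and 55% of studies in which VO2peak passes the screen there.

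A reader might also infer that the regression is not hierarchical. The text does not show this: screening decides which variables enter, and those retained could still be ordered on theoretical grounds. What can be said is that the order is not stated.

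**Conclusion.** The point holds as a conditional risk created by a stated rule, and it is worth correcting before analysis. Crude significance is the only stated route into the model, it applies to factors the protocol calls known, and nothing else in the plan adjusts for them. Independence is therefore not assured.

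The size depends on assumptions the documents cannot settle. With equal, offsetting effects of 0.3, loss of a real determinant runs from 1% with no correlation to about 61% at -0.6. Joint loss of both is less common, from 0% to about 30%, so the usual failure is a model holding one of the two with a biased coefficient. Unequal effects change the form of the problem: the stronger variable is rarely dropped, but its coefficient is distorted because the weaker one is usually missing. The sample size figures are unaffected.

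**What to change.** Before analysis, name a first block of known determinants that enters the regression whatever the crude P values, for example age, sex, physical activity, diet composition and VO2peak. All are already collected. Age is not on the background's list, so the sponsor should justify the final set. Muscle characteristics come only from optional biopsies, so they cannot serve in a block meant for all participants.

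Test each further candidate by adding it to that block, and report the adjusted estimate with its 95% CI. Keep the crude correlations as description only. Report models with and without VO2peak, because it may mediate the association of physical activity with fat use.

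The cost is a change of wording, a few degrees of freedom out of about 190, and some loss of precision from collinearity within the block. No new data are needed, and the plan's second sample size method already allows for ten predictors.
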